
cost of surgery and aftercare in surgical patients, we believe that this project will establish the ground-work necessary to develop a sustainable clinical program for other surgical practices to minimize post-surgical complications and overall costs.

2. Objectives (include all primary and secondary objectives)

1. Evaluate whether an intensive pre- post-surgical smoking cessation intervention will promote smoking cessation both pre- and post-surgery.

Hypothesis: An intensive smoking intervention will promote smoking abstinence across the pre- and post-surgical phases. Secondary outcomes will include cessation at 1-month postsurgical follow up and other smoking-related outcomes (withdrawal, craving).

2. Assess whether changes in smoking are associated with surgical recovery outcomes.

Hypothesis: Patients who show longer periods of sustained smoking abstinence pre- and post-surgery will have better recovery post-surgery as evidenced by the following outcomes: shorter length of stay, fewer admissions to the ICU, lower total cost of procedure, smaller total quantity of opioid analgesic use, and lower 30-day hospital readmission rates.

3. Examine baseline decision-making characteristics, including smoking motivation, delayed discounting, and distress tolerance, as predictors of post-surgical recovery and smoking cessation outcomes.

Hypotheses: (1) Patients with strongest positive and negative reinforcement-based smoking motives (i.e., patients whose motives to smoke center around experiencing the positive outcomes of smoking, such as mood enhancement and/or ameliorating the cons of abstaining from smoking, including craving and negative affect) will be most likely to resume smoking post-surgery. (2) Patients with steeper discounting curves at study baseline and/or lower distress tolerance will be less likely to abstain from smoking pre-surgery, may request higher quantities of opioid analgesics post-surgery, and will be at the greatest risk of relapsing to smoking post-surgery.

The overall objective of this study is to assess the feasibility of conducting a pre-postoperative smoking cessation study in presurgical patients. If a positive signal is found, then these data will be used to support a large-scale grant application to evaluate this approach using a randomized, controlled study design.

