5. Study Procedures

- a. Study design, including the sequence and timing of study procedures (distinguish research procedures from those that are part of routine care).

In this two-year open-label feasibility study, 20 smokers who are planning to undergo elective surgery will complete a 12-week intensive pre- post-surgical smoking cessation intervention, involving three major components: (1) varenicline administration, (2) standardized smoking cessation counseling, and, during the pre-surgery phase, (3) incentives for urine samples that test negative for cotinine. Upon verifying that all study eligibility criteria are met, patients will enter the intervention phase of this study. During this phase, patients will attend weekly study visits to receive the pre-surgical component of the intensive smoking cessation intervention in approximately the 4-6 weeks leading up to surgery, and complete approximately six additional weekly study visits post-surgery in order to continue with the post-surgical varenicline administration component of the intensive smoking intervention for a total of 12 weeks, and to allow for in-person assessment of post-surgical smoking cessation and surgical recovery outcomes. Finally, participants will be scheduled for an in-person follow-up visit approximately one month following completion of the study to assess study outcomes. In some cases, this follow-up period may extend as long as six months to collect data that ensures study outcomes are being met.

Recruitment: We will recruit participants via physician or self-referrals. A number of strategies may be utilized to identify potential participants early in the elective surgical process. We will provide medical departments and physicians detailed information about study eligibility criteria and procedures and encourage them to provide potentially eligible patients with information to contact the study team. We will also post flyer advertising a smoking cessation study for elective surgical patients in common areas and waiting rooms to enable potential participants to contact us directly. All interested individuals will be instructed to call the study team and complete a brief phone screen to establish initial study eligibility before conducting a full screening visit.

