Screening: We are proposing to screen 40 individuals and complete 20 people for this initial study, which is consistent with other pilot/feasibility studies and will provide enough data to indicate whether a signal exists that would support further evaluation of this treatment approach in a larger-scale clinical trial study.

All participants will read and sign the informed consent with a trained staff member before conducting the screening visit, which will include self-report of smoking and other related variables, urinalysis verification of recent smoking, illicit drug, and pregnancy status, a medical history to determine medical eligibility, and completion of baseline decision-making measures. Participants will also provide written permission for study staff to access medical records to verify postsurgical outcomes and analgesic use, for study outcome measures.

Screening and Study-related Measures:

The following measures will be utilized during the study to determine eligibility and provide data necessary to complete the study aims. Individuals enrolled into the study will complete assessments weekly during treatment with one follow-up assessment 30 days after study completion. These data will be used to monitor changes in smoking status, mood or behavior changes related to medication or tobacco abstinence, health and pain-related outcomes, and vital signs.

- Time-Line Follow-Back (TLFB; Sobell et al., 1988): a validated self-report measure to record daily behaviors, including medication compliance and use of tobacco, alcohol, and other drugs/medications.

A past 30-day assessment will be conducted at baseline, with weekly assessments during the study

- Smoking History: brief self-report questionnaire of smoking history, quit attempts, use of pharmacotherapy, interest in quitting smoking, perceived ability to quit smoking and perceived health risk of smoking.
- Fagerström Test for Nicotine Dependence (FTND; Heatherton et al., 1991): 6-item self-report measure of nicotine dependence.
- Contemplation Ladder (Biener & Abrams, 1991): graphical description of process of change in relation to the need to quit smoking. Score ranges from 0 (no thoughts of quitting) to 10 (taking action to quit).
- Minnesota Nicotine Withdrawal Questionnaire-Revised (MNWQ-R; Hughes & Hatsukami, 1986): The 15- item self-report measure of nicotine withdrawal with good reliability and validity.

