Following the surgery, patients will resume weekly study visits approximately two weeks post-surgery in order to continue with the post-surgical varenicline administrations and to assess post-surgical recovery and smoking cessation outcomes. We will attempt to coordinate with the surgery team to schedule patients' first post-surgical study visit on the same day as their two-week post-surgical follow-up visit with their surgeon

in order to maximize convenience for patients, and participants will be given a 2-week supply of varenicline at the study visit immediately prior to their scheduled surgery so that they can continue taking the full dose while recovering from surgery. Patients will return weekly for a total of six post-surgical study visits. Additional follow-up may occur for six months post-intervention. More details about timing of each of the intervention components are listed below:

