Study Visits: Participants will attend an initial in-person screening visit, described above, and will return to the clinic on approximately a weekly basis during study weeks 1-12 to receive the intensive pre- post-surgical smoking cessation intervention. Visits during the surgical week will occur prior to the surgery to allow for postsurgical recovery time and we will provide 2 weeks of medication at that visit to allow participants to continue using the medication during their recovery period and provide general flexibility to participants who are unable to complete a visit during their first postsurgical week. Each visit will include collection of a urine sample (that will be tested for urinary cotinine and illicit drug use), a breath CO sample, and self-report questionnaires. None of the data collected during study visits will be shared with the patients' surgical team. Participants will be contacted via phone approximately 3 weeks after study

completion and asked whether they are still abstaining from smoking. Those who endorse continued abstinence will be asked to complete a follow-up visit, during which they will provide a urine sample that will be tested for evidence of cotinine. Participants may be contacted over an additional six month period for follow-up questions pertaining to treatment outcome. Participants will be compensated for attending study visits and completing brief questionnaires and tasks; session payment values will escalate after surgery to encourage continued retention (a standard practice in our treatment protocols) and the total possible study visit compensation will be \$650.

- c. Blinding, including justification for blinding or not blinding the trial, if applicable.

Given that this is an open-label pilot study, all participants will receive the same intensive pre to post-surgical smoking cessation intervention in order to collect the data necessary to illustrate the feasibility of incorporating such an intensive intervention into the hospital setting. This pilot data will be used to support the need for future funding to complete larger randomized controlled trials, and/or multi-site trials. Given that no comparison condition is being included in the current pilot study, the issue of blinding is not applicable at this time.

- d. Justification of why participants will not receive routine care or will have current therapy stopped.

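### The one-month follow-up is open to all participants in Section 5a but only to self-reported abstainers in Section 5b, and the follow-up abstinence rate has no stated denominator

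*Combined protocol and SAP*

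**What the plan says.** Three places describe who is seen at follow-up.

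- Section 5a, study design: "participants will be scheduled for an in-person follow-up visit approximately one month following completion of the study to assess study outcomes". No abstinence condition is attached.
- Section 5a, Screening and Study-related Measures: "Individuals enrolled into the study will complete assessments weekly during treatment with one follow-up assessment 30 days after study completion". The stated purpose is wider than smoking alone: "These data will be used to monitor changes in smoking status, mood or behavior changes related to medication or tobacco abstinence", with health, pain and vital signs also listed.
- Section 5b, Study Visits: participants are phoned about three weeks after completion and "asked whether they are still abstaining from smoking". The next sentence reads: "Those who endorse continued abstinence will be asked to complete a follow-up visit, during which they will provide a urine sample".

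Section 8a defines abstinence at follow-up as point prevalence, requiring both a cotinine-negative sample and a self-report of seven days without smoking. Section 8c describes the analysis as mostly descriptive. Neither section names the denominator for the follow-up rate, or says how to classify people who report smoking, cannot be reached or do not attend.

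Objective 1 in Section 2 places the outcome among the secondary ones and dates it differently: "Secondary outcomes will include cessation at 1-month postsurgical follow up and other smoking-related outcomes (withdrawal, craving". Sections 5a and 5b count from study completion.

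**The concern.** Staff cannot follow both rules. If they follow Section 5b, the follow-up outcome is observed selectively, in people chosen by their own report on nearly the same variable.

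The screening question also differs from the endpoint. Asking whether someone is still abstaining asks about unbroken abstinence. The endpoint asks only about the last seven days and a urine test.

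Because the analysis is descriptive, the reported percentage is itself the result. Section 2 says the data will support a grant application for a randomized study if a signal is seen, and Section 4 names maintenance of abstinence after surgery as one of the gaps to be addressed. A follow-up rate whose meaning depends on which section staff followed and which denominator the analyst chose is a weak basis for either purpose.

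**Working it through.** The plan states no follow-up rate, so there is no figure to reproduce. The check compares the rules and shows how far the result can move.

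**1. Gate against endpoint.** Take each type of participant at the phone call.

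| Status at the call | Could meet the Section 8a endpoint? | Seen under Section 5a? | Seen under Section 5b? |
|---|---|---|---|
| Abstinent throughout | Yes | Yes | Yes |
| Lapsed, then quit again | Yes, if smoke-free for 7 days with negative cotinine | Yes | No, if the question is answered literally |
| Smoking | No | Yes, for the other measures | No |
| Not reached by phone | Unknown | May still be lost | No |

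The gate costs the urine test in the second row and the in-person measures in the second and third. The fourth row is mostly not its doing, because people who cannot be reached may be missing under either rule.

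**2. Denominator.** Inputs: 20 planned completers (Section 5a, Screening; Section 8c). The number invited and attending, k, and the number verified, m, are assumptions, since the documents give neither. The two candidate rates are m/k and m/20, and their ratio is (m/k) / (m/20) = 20/k. Holding verification at 75% of those invited, with exact (Clopper-Pearson) 95% intervals:

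| k | m | m/k | m/20 | 20/k |
|---|---|---|---|---|
| 4 | 3 | 75% (19.4 to 99.4) | 15% (3.2 to 37.9) | 5.0 |
| 8 | 6 | 75% (34.9 to 96.8) | 30% (11.9 to 54.3) | 2.5 |
| 12 | 9 | 75% (42.8 to 94.5) | 45% (23.1 to 68.5) | 1.67 |
| 16 | 12 | 75% (47.6 to 92.7) | 60% (36.1 to 80.9) | 1.25 |

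The two rates agree only when k = 20.

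Completers are not the only possible full denominator. If 25 or 30 people start (assumed) and no non-completer is verified, m = 6 gives 6/25 = 24% or 6/30 = 20%.

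**3. Untested re-quitters.** With 20 as denominator, each re-quitter who would have tested negative is worth 1/20 = 5 percentage points. In the k = 8, m = 6 case, if r of the other 12 are in that position and r runs from 0 to 3 (assumed), the rate with everyone invited is (6 + r)/20, or 30% to 45%.

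**4. Time anchor.** Thirty days is 30/7 = 4.3 weeks. The interval from surgery to a visit 30 days after completion depends on the schedule text used:

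- Section 5a, intervention: "patients will resume weekly study visits approximately two weeks post-surgery", with six weekly visits in all. The sixth falls at 2 + 5 = 7 weeks, and follow-up at 7 + 4.3 = 11.3 weeks.
- Table 2: last pre-surgical visit in week 6, last visit in week 12. With surgery soon after the week 6 visit, follow-up is at about (12 - 6) + 4.3 = 10.3 weeks.
- Section 4: medication continues 4 to 6 weeks after surgery. If completion means the end of medication, follow-up is at 4 + 4.3 = 8.3 to 6 + 4.3 = 10.3 weeks.

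The visit therefore falls roughly 8 to 11 weeks after surgery, against 4.3 weeks if one month is counted from surgery. Under the Section 5a schedule, one month after surgery lies within the weekly visits, where there is no gate and medication continues. The two anchors therefore describe different outcomes.

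**The case against.** The best defence is that Section 5b describes a verification step. Everyone is phoned, those who admit smoking are counted as not abstinent, and only claims of abstinence need a urine test. The Section 8a definition is compatible with this. It does not dispose of the point: no section states the convention, it leaves people who are not reached or do not attend unclassified, it misses re-quitters, and it still contradicts Section 5a.

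Several stronger readings are tempting but unsupported.

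- A reader might infer that the plan will report an inflated rate among attenders. No section proposes that denominator; the defect is that none is named.
- A reader might infer that the study can no longer learn who relapses. Objective 3 asks which patients "will be at the greatest risk of relapsing to smoking post-surgery", but its predictors are measured at baseline, the phone call is put to everyone, and up to 12 weekly visits with urine, breath and questionnaire data have no gate. The loss is confined to in-person data at one time point. Nor does Section 8c say that its analysis of change over time relies on the follow-up visit.
- A reader might take the $650 visit total, which includes the $50 follow-up payment, as proof that everyone was meant to attend. It is a maximum, and Section 5b quotes it alongside the gate, so it settles nothing.
- A reader might want to state a loss of precision for comparing smokers with abstainers at follow-up. That would rest on invented group sizes and on a comparison the plan does not specify.

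It is also fair to say that some re-quitters might answer yes on the phone and be invited after all. Their number is unknown either way.

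**Conclusion.** The contradiction is plain on the text, and the denominator is missing. Following Section 5b as written makes the follow-up outcome selectively observed and applies a continuous-abstinence screen to a seven-day endpoint.

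The factor of 20/k holds for any number invited when the alternatives are invitees and 20 completers. The particular percentages (75% or 30%, and 30% to 45% with re-quitters) rest on assumed counts and serve only as illustration. The 8-to-11-week timing rests on the plan's own schedules, read with completion as the last visit or the end of medication.

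The weight is moderate. The outcome is secondary in a mostly descriptive feasibility study of 20 completers, and no test or sample size changes. It should be fixed because the correction is simple and the rate cannot be interpreted without it.

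**What to change.** 1. Reconcile Section 5b with Section 5a: invite participants to the one-month visit whatever they answer on the phone. The call can remain as a reminder and a record of self-report.
2. State in Section 8 that follow-up point prevalence is reported over all who started the intervention, and report that number. Count anyone not verified, including those not reached or not attending, as not abstinent. Give the rate among completers as a sensitivity analysis. Participants who leave early have no completion date from which to count a month; they stay in the denominator, and the plan should say whether a visit is attempted.
3. Align Objective 1 with Sections 5a and 5b by using one time anchor, study completion, for the one-month outcome.

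The cost is mainly wording. Each added visit carries the $50 already listed in Table 2: 12 x $50 = $600 if 12 more people attend, or (30 - 8) x $50 = $1,100 if 30 started, 8 would have come anyway and all the rest attend (assumed counts). The headline rate may be lower, since counting unverified people as not abstinent is deliberately conservative. Some lapsed participants will decline, so the in-person data at follow-up will improve but may remain incomplete.

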2. Varenicline: Varenicline will be administered as clinically indicated and will begin approximately 4-6 weeks prior to surgery. All participants will receive a 1-week dose induction period (0.5mg QD Days 1-3, 0.5mg BID Days 4-7) before transitioning to a full maintenance dose (1mg BID). The target-quit date (TQD) will be on Day 8 (week 2) and will coincide with the 1st day of the maintenance dose, consistent with recommended guidelines. Participants will receive a 1-week supply of varenicline (with 3 days of extra doses in the event of an unpredicted event) in blister packs at each study visit. This will enable us to better track medication adherence and adverse events, and will help encourage participants to attend weekly visits. There is nothing experimental about the use of varenicline in this study. Participants will receive a 2-week supply of varenicline (with 3 days of extra doses) at the visit immediately prior to the participants’ scheduled surgery in order to allow participants to continue taking the full maintenance of varenicline uninterrupted, while also allowing for ample healing time before returning for the first study visit post-surgery.

3. Incentives: Incentive payments will begin on the TQD (week 2) and will be in place for 5 weeks or until surgery (whichever is sooner). Participants will receive monetary based incentives for biochemical evidence of smoking abstinence. Abstinence will be determined via breath carbon monoxide (CO) ratings during Week 2, and via urinary cotinine for the duration of the study. The transition from CO to cotinine is a common procedure that provides a method for awarding incentives to participants who have recently begun abstaining from smoking but will still test positive for cotinine (because of the long elimination half-life of cotinine). Cotinine-based testing will be used as the definition of abstinence during weeks 3-12. CO will be tested using mobile meters and abstinence will be

Table 2. Incentive and Compensation Structure

Study Week	Study Visit	Incentives	Visit Payments
Screening			\$30
1	-6		\$20
2	-5	\$20	\$20
3	-4	\$40	\$20
4	-3	\$60	\$20
5	-2	\$80	\$20
6	-1	\$100	\$20
7	1		\$50
8	2		\$60
9	3		\$70
10	4		\$80
11	5		\$90
12	6		\$100
Follow-up			\$50
Total:		\$300	\$650

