defined as ≤ 4 ppm. Cotinine will be tested using hand-held dipsticks and abstinence will be defined as ≤ 100 ng/ml. Incentives will be awarded immediately onsite for biochemical samples that meet the abstinence criteria during weeks 2-6. Table 2 displays the schedule of payments, which have been arranged strategically to maximize the impact of the incentives. In other words, research has shown that incentive payments that escalate over time, are high in magnitude, and include reset contingencies for positive samples are the most effective in promoting behavior change. Total possible incentive payments will be \$300. Though this value may seem high, it is important to make the incentive magnitude for this initial study high enough to determine whether it will produce the expected effect on smoking cessation and to accurately assess the study outcome measures; future studies can be conducted that vary the magnitude of the incentive to reduce overall cost of the intervention. Further, this approach will help us to determine whether the cost expenditure associated with this study will be recovered by the cost savings that we hypothesize will result from smoking cessation and the associated decrease in complications, analgesic use, and hospital readmissions, which run in thousands of dollars per complication.

In addition to the visit payments and incentives displayed in Table 2, participants will have the chance to win \$5 in bonus money at the end of each session that includes an administration of the PASAT to assess distress tolerance.

Biochemical Testing: It is important to note that results of biochemical testing will not be conveyed with the surgical team. The reason for this is that we need to ensure that patients will not falsify or attempt to misrepresent their smoking status out of concern that their results may have a negative impact on their surgery plans. All results obtained from these patients will be kept confidential from the surgical team and the surgical team will continue to assess smoking in the manner that had been used prior to the study.

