There is no standard and/or routine access to smoking cessation in elective surgical patients. This study will not disrupt any ongoing routine care associated with the participant's surgery.

- e. Justification for inclusion of a placebo or non-treatment group.

N/A

- f. Definition of treatment failure or participant removal criteria.

Participants failing to continue to meet any of the inclusion/exclusion criteria will be removed from the study and an appropriate clinical referral provided. For example, subjects developing a psychiatric disorder or symptoms requiring treatment (e.g., mania, suicidality, and psychosis), major medical illnesses or serious injuries, which would preclude further participation, will be withdrawn. Subjects who consistently fail to show up for the first treatment session may also be withdrawn.

- g. Description of what happens to participants receiving therapy when study ends or if a participant's participation in the study ends prematurely.

Participants will be debriefed after completing the 1-month follow-up, 6-month follow-up, or premature removal. They will be fully informed about all treatment options for smoking cessation and provided with additional referrals as needed. Any participant who is discharged or voluntarily leaves the study will be provided referrals for obtaining assistance with smoking cessation. The participants will continue meeting with their surgical team, consistent with routine practice for post-surgical patient care and independent of the study.

6. Inclusion/Exclusion Criteria

Inclusion Criteria: We will recruit cigarette smokers who have scheduled an elective surgery to participate in the study. Inclusion criteria will include having a surgery scheduled 5-10 weeks in advance, reporting regular cigarette smoking (smoking 3 times a week or more) and providing a cotinine-positive urine sample.

Exclusion Criteria: Exclusion criteria will include being contraindicated for varenicline use, using products other than cigarettes as a primary nicotine product (including e-cigarettes), providing an illicit drug-positive urinalysis test without evidence of concurrent prescription (e.g., for narcotic pain medications, for example), being pregnant or breastfeeding, or a score >20 on the Beck Depression Inventory-II or a score ≥ 0 on the suicide question of the BDI, past year suicidal ideations or behavior on the C-SSRS, being

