- b. Justification and safety information if FDA approved drugs will be administered for non-FDA approved indications or if doses or routes of administration or participant populations are changed.

N/A

- c. Justification and safety information if non-FDA approved drugs without an IND will be administered.

N/A

8. Study Statistics

Outcome Measures: We will collect a variety of outcome measures to enable a full characterization of decision-making factors at baseline, and the impact of this intervention on smoking status, postsurgical outcomes, opioid analgesia utilization, and cost.

- a. Primary outcome variable.

Smoking Outcomes: Our primary outcome variable will be smoking status. Smoking abstinence will be defined as a negative biochemical sample + self-report of no smoking for the past 7 days, mean % negative samples, and mean continuous negative samples. Smoking will be evaluated within each pre and post-surgical phase, and collapsed over the 11-week targeted cessation period (following the TQD during week 2). Point prevalence smoking abstinence at the follow-up will be defined as a negative cotinine sample + self-report of no smoking for the past 7-days.

b. Secondary outcome variables.

Secondary smoking outcomes will include ratings of nicotine withdrawal and craving, using standardized measures, and frequency of adverse events judged to be related to varenicline or smoking cessation.

Surgical Recovery Outcomes: A variety of postsurgical outcomes will be evaluated. These will include length of hospital stay, overall quantity and frequency of opioid analgesic use, pain ratings of during the recovery period, types and frequency of post-operative complications, frequency of admission into the intensive care unit, and 30-day hospital readmission rates.

c. Statistical plan including sample size justification and interim data analysis.

Since this is an open-label study design, results will be analyzed in a mostly descriptive method.

Smoking Outcomes: Smoking outcomes will be evaluated as a function of time over the 11-week intervention. Smoking cessation rates will also be compared from the pre to post-intervention phases.

Surgical Recovery Outcomes: Surgical outcomes will be evaluated as a function of percent biochemically-confirmed smoking abstinence, to assess whether the duration and/or magnitude of smoking abstinence is statistically associated with 30-day readmission rates, opioid analgesic use, and other surgical outcomes.

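### The removal rule in Section 5.f, followed as written, removes participants who reach the primary outcome, and the plan does not say how removed participants are counted

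*Combined protocol and SAP*

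**What the plan says.** **Removal rule, Section 5.f.** "Participants failing to continue to meet any of the inclusion/exclusion criteria will be removed from the study". The next sentence illustrates the rule without limiting it: "For example, subjects developing a psychiatric disorder or symptoms requiring treatment (e.g., mania, suicidality, and psychosis", followed by major medical illness and serious injury.

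**Entry criteria, Section 6.** "Inclusion criteria will include having a surgery scheduled 5-10 weeks in advance", and then "reporting regular cigarette smoking (smoking 3 times a week or more) and providing a cotinine-positive urine sample". The exclusions include an illicit-drug-positive urine without a prescription, a main nicotine product other than cigarettes, and a raised depression score.

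**Primary outcome, Section 8.a.** "Smoking abstinence will be defined as a negative biochemical sample + self-report of no smoking for the past 7 days", evaluated before and after surgery.

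**Treatment of quitters elsewhere.** Section 5.a says "Cotinine-based testing will be used as the definition of abstinence during weeks 3-12" and "Incentives will be awarded immediately onsite for biochemical samples that meet the abstinence criteria during weeks 2-6". Section 5.b invites those who report continued abstinence to a follow-up visit with a urine cotinine test.

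**Repeat measurement.** Section 5.b: "Each visit will include collection of a urine sample (that will be tested for urinary cotinine and illicit drug use". The depression inventory is also repeated at every visit (Section 5.a).

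**Denominator.** Section 8.c sets the sample at 20 completers. Section 5.g provides debriefing and referral after premature removal. Neither section says whether removed participants are still assessed or how they count.

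**The concern.** Section 5.f turns entry criteria into continuing conditions and makes removal mandatory. Two of those conditions, regular smoking and a positive cotinine, are what the intervention is meant to end. On its face, the rule treats success as a reason for removal.

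Setting that aside as a slip leaves a practical problem. Staff must decide unaided which criteria continue. Some candidates are re-measured during the study or bear directly on smoking. This is a single-arm study with a mostly descriptive analysis, so the abstinence rate is its main result. If people leave for reasons related to smoking and the rate is taken over those who complete, the result depends partly on how the removal rule was read.

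**Working it through.** No figure in the plan depends on the rule, so the main check sets the provisions side by side. Two small calculations follow.

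**1. Consistency of the text.**

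| Provision | What it requires of a participant who has quit |
|---|---|
| 5.f with the smoking and cotinine criteria of Section 6 | Removal |
| 5.a, incentives | Payment for negative samples in weeks 2-6 |
| 5.a, biochemical definition | Cotinine assessment in weeks 3-12 |
| 8.a | Evaluation before and after surgery |
| 5.b | Invitation to a follow-up visit |

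The first row cannot hold together with the other four. No section says that the smoking and cotinine criteria apply at screening only.

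**2. The payment table.** Table 2 adds up.
- Incentives: 20 + 40 + 60 + 80 + 100 = $300.
- Visit payments: 30 + 6 × 20 + (50 + 60 + 70 + 80 + 90 + 100) + 50 = $650.

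Suppose a quitter were removed at the first negative cotinine, in week 3. The most that person could earn is 20 + 40 = $60 of the $300 in incentives and 30 + 3 × 20 = $90 of the $650 in visit payments. The full $300 needs negative samples throughout weeks 2-6, so the table presumes that quitters stay.

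**3. Literal removals, for illustration only.** Expected removals = 20 × quit rate. Assumed rates of 20%, 40% and 60% give 4, 8 and 12 of 20. Only 60% appears in the protocol (Section 4), as an upper figure for short-term cessation with incentives in hard-to-treat populations. It is not a forecast for this study.

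**4. Removal on a sensible reading.** Let N = 20 start treatment, a = 10 be truly abstinent, r be removed, and s of those removed be abstinent. The rate among those remaining is (a − s)/(N − r). The values of a, r and s are assumptions.

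| r | s | Rate among those remaining | Removed kept in denominator and counted as smoking, (a − s)/N |
|---|---|---|---|
| 2 | 0 | 10/18 = 55.6% | 10/20 = 50% |
| 2 | 1 | 9/18 = 50% | 9/20 = 45% |
| 2 | 2 | 8/18 = 44.4% | 8/20 = 40% |
| 4 | 0 | 10/16 = 62.5% | 10/20 = 50% |
| 4 | 2 | 8/16 = 50% | 8/20 = 40% |
| 4 | 4 | 6/16 = 37.5% | 6/20 = 30% |

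The true rate is 10/20 = 50% in every row. The error among those remaining can go either way. Restoring the denominator while counting all removed participants as smokers is not enough if some of them were abstinent. Only continued assessment recovers 10/20 in every row.

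**5. Related provisions.** Section 5.a ties the depression-score exclusion to screening. Section 9.b answers later endorsement of suicidal thoughts on the inventory with a fuller suicidality assessment, and lets some participants who stop the drug for side effects remain in the study. Section 9.a leaves continuation of study drug after hospitalization to the medical monitor. Sections 9.a and 9.b make withdrawal for pregnancy mandatory. These graded responses do not fit a blanket rule of removal for ceasing to meet any criterion.

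**The case against.** The strongest reply is that nobody would apply the rule literally. Section 5.a verifies eligibility before the intervention phase and places the urine check of recent smoking at screening. The examples in 5.f concern psychiatric or medical deterioration. The incentives, outcome definition and follow-up all presume that quitters stay. This stands: the wording is very probably a slip. A reader might infer that the trial cannot observe its own primary outcome, and the documents as a whole do not support that. What remains is a mandatory sentence that contradicts the outcome, with no exemption for the smoking and cotinine criteria.

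Four other strong inferences also fail or weaken.
- **Surgery timing.** A reader might say that the 5-10 week criterion lapses for everyone as surgery approaches. It can equally be read as booking lead time at enrolment, which does not lapse. It needs clarifying, but the point does not rest on it.
- **Depression score.** A later raised score might seem to trigger removal. Section 5.a limits that exclusion to screening, so the clearer examples are the repeated drug screen and a change of main nicotine product.
- **Upward bias.** This requires those removed to be disproportionately smokers and to leave the denominator. The plan establishes neither. A drug-positive abstainer who is removed would lower the rate.
- **Variation between sites.** The protocol describes one clinic. The discretion lies with its study staff.

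It is also fair to say that an unstated denominator affects every dropout. The removal rule adds to that problem because removal is imposed by the study and may be related to the outcome.

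**Conclusion.** The point holds in limited form. Section 5.f as written conflicts with the primary outcome, the incentive schedule, the cotinine definition for weeks 3-12 and the follow-up of abstainers. Literal application is unlikely. On a sensible reading, removal linked to the outcome remains possible, and the plan neither keeps removed participants under assessment nor says how they count towards a target defined by completers.

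Under the assumptions shown (2 to 4 of 20 removed, true rate 50%), the rate among those remaining could range from 37.5% to 62.5%. That range shows what the gap permits. It does not estimate a bias, and neither direction nor size can be determined from the documents. The correction is still worth making before the rule is used, because a stated mandatory rule gives a wrong result and the remedy is cheap.

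**What to change.** 1. Amend Section 5.f to state that the smoking, cotinine and surgery-timing criteria are verified at entry only.
2. The sponsor should reconcile 5.f with Section 6, the screening text for the depression inventory in Section 5.a, and the provisions in Sections 9.a and 9.b on hospitalization, suicidality, stopping the drug and pregnancy. The text should say which remaining criteria continue to apply. Which clinical withdrawal rule should hold is for the sponsor to decide.
3. Separate stopping treatment from stopping outcome collection. Continue the smoking assessments already planned for removed participants who agree.
4. In Section 8.c, define the abstinence denominator as everyone who started treatment. State in advance how missing outcomes count, and report the number removed with reasons. Give the rate under both extremes for those not assessed: all smoking and all abstinent.

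The cost is a short amendment plus some continued contact with removed participants, with no new measurements. The reported abstinence rate may be somewhat lower than one calculated among completers.
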